6.1.4.8 HYPERTENSION

Hypertension is a common class effect of drugs that inhibit VEGF pathways and has been reported in subjects treated with cabozantinib. Blood pressure (BP) should be monitored in a constant position at each visit (either sitting or supine) and every day at home by the patients himself.

Treatment guidelines for hypertension deemed related to study drug are presented in Table 4. In general, subjects with known hypertension should be optimally managed prior to study entry. Decisions to decrease or hold the dose of study treatment must be based on BP readings taken by a medical professional and must be confirmed with a second measurement at least 5 minutes following the first measurement. Other than for hypertension requiring immediate therapy, the presence of new or worsened hypertension should be confirmed at a second visit before taking therapeutic action. It is recommended that this second visit occurs within 1 week.

Table 4 Guidelines for the Management of Treatment-emergent Hypertension

| Criteria for Dose Modification ^a | Dose Modification |
|---|--|
| > 150 mm Hg (systolic) and < 160 mm Hg OR > 100 mm Hg (diastolic) and < 110 mm Hg | 
 Optimize antihypertensive treatment by adding new or additional antihypertensive medications and/or increase dose of existing medications. Reduce study treatment by one dose level if optimal antihypertensive therapy (usually to include 3 agents) does not result in BP < 150 mm Hg systolic or < 100 mm Hg diastolic, If subject is symptomatic interrupt study treatment |
| ≥ 160 mm Hg (systolic) OR ≥ 110 mm Hg (diastolic) | 
 Reduce study treatment by 1 dose level Add new or additional antihypertensive medications and/or increase dose of existing medications and monitor subject closely for hypotension. If optimized |

| | |
|--|--|
| | 
antihypertensive therapy (usually to include 3 agents) does not result in BP < 150 mm Hg systolic or < 100 mm Hg diastolic, study treatment should be dose reduced further or interrupted
 
• Study treatment should be dose interrupted if upper limits of BP (\geq 160 mm Hg systolic or \geq 110 mm Hg diastolic) are sustained and not adequately manageable or if BP is > 180 mm Hg systolic or > 120 mm Hg diastolic or if subject is symptomatic.• Restart study treatment at the most tolerable dose and reescalate only if BP falls to and is sustained at < 140 mm Hg systolic and < 90 mm Hg diastolic. |
| Hypertensive emergency ^b or hypertensive encephalopathy | 
• Discontinue study treatment |

^a The investigator may decide to initiate or adjust antihypertensive treatment at a lower threshold than systolic BP > 150 mm Hg or diastolic BP > 100 mm Hg based on their clinical judgment and assessment of the individual subject.

^b Hypertensive emergency is defined as uncontrolled elevated blood pressure with clinical evidence of progressive or impending end-organ damage (ie, myocardial infarction/ischemia, intracranial hemorrhage, cerebral ischemia, pulmonary edema, encephalopathy, kidney damage)

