5.2 EXCLUSION CRITERIA

5.2.1 MEDICAL HISTORY AND CONCURRENT DISEASES

- Fibrolamellar carcinoma or mixed hepatocellular cholangiocarcinoma
- Radiation therapy (eg, I-131 or Y-90) within 4 weeks (2 weeks for radiation for bone metastases) or radionuclide treatment within 6 weeks of starting therapy (subject is excluded if there are any clinically relevant ongoing complications from prior radiation therapy)
- Prior cabozantinib treatment
- Known brain metastases or cranial epidural disease unless adequately treated with radiotherapy and/or surgery (including radiosurgery) and stable for at least 3 months before starting therapy. Eligible subjects must be without corticosteroid treatment at the time of starting therapy.
- Concomitant anticoagulation, at therapeutic doses, with anticoagulants such as warfarin or warfarin-related agents, low molecular weight heparin (LMWH), thrombin or coagulation factor X (FXa) inhibitors, or antiplatelet agents (eg, clopidogrel). Low dose aspirin for cardioprotection (per local applicable guidelines), low-dose warfarin (≤ 1 mg/day), and lowdose LMWH are permitted.
- The subject has uncontrolled, significant intercurrent or recent illness including, but not limited to, the following conditions:
 - a. Cardiovascular disorders including:
 - i. Symptomatic congestive heart failure, unstable angina pectoris, or serious cardiac arrhythmias
 - ii. Uncontrolled hypertension defined as sustained BP > 150 mm Hg systolic, or 100 mm Hg diastolic despite optimal antihypertensive treatment
 - iii. Stroke (including TIA), myocardial infarction, or another ischemic event within 6 months before starting therapy

- iv. Thromboembolic event within 3 months before starting therapy. Subjects with thromboses of portal/hepatic vasculature attributed to underlying liver disease and/or liver tumor are eligible
- b. Gastrointestinal (GI) disorders including those associated with a high risk of perforation, or fistula formation:
 - i. Tumors invading the GI tract, active peptic ulcer disease, inflammatory bowel disease (eg, Crohn's disease), diverticulitis, cholecystitis, symptomatic cholangitis or appendicitis, acute pancreatitis or acute obstruction of the pancreatic duct or common bile duct, or gastric outlet obstruction
 - ii. Abdominal fistula, GI perforation, bowel obstruction, intra-abdominal abscess within 6 months before starting therapy
- Note: Complete healing of an intra-abdominal abscess must be confirmed prior to starting therapy

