6.1.4 DOSE MODIFICATIONS

6.1.4.1 CABOZANTINIB DOSE MODIFICATIONS

Cabozantinib dose reduction

Toxicities will be graded using the NCI CTC version 5.0 (see Appendix 4). All dose modifications will follow pre-defined dose levels as indicated below.

The modifications of cabozantinib dosage will follow the following pre-defined dose levels:

Table 1: Cabozantinib dose reduction

| | | |
|------------------------------|----------|--|
| Dose level 0 (standard dose) | 60 mg po | 1 tablet of cabozantinib every day |
| Dose level -1 | 40 mg po | 1 tablet of cabozantinib every day |
| Dose level -2 | 20 mg po | 1 tablet of cabozantinib every day |
| Dose level -3 | 20 mg po | 1 tablet of cabozantinib every 2 or 3 days |

If a patient experiences several toxicities and there are conflicting recommendations, the recommended dose adjustment, which reduces the dose to the lowest level, should be used.

If a dose reduction has been performed, intra-subject dose re-escalation can be considered (up to the maximum of 60 mg daily dose) at the discretion of the treating investigator provided that the toxicities has resolved to at least CTC-Grade baseline levels.

Table 2 Dose Modification Criteria

| Toxicity | Criteria Recommended Guidelines for Management |
|---|--|
| Grade 1 AEs | Continue study treatment if AE is tolerated |
| Grade 2 AEs which are intolerable and cannot be adequately managed | At the discretion of the investigator, study treatment should be dose reduced or interrupted. Note: It is recommended that dose interruptions be as brief as possible. |
| Grade 3 (except clinically non-relevant laboratory abnormalities) | Study treatment should be interrupted unless the toxicity can be easily managed with a dose reduction and optimal medical care. |
| Grade 4 AEs (except clinically non-relevant laboratory abnormalities) | Subjects should have their study treatment interrupted immediately. Discontinue study treatment unless the following criteria are met: Subject is deriving clear clinical benefit as determined by the investigator and agreed by the Sponsor. Toxicity can be managed with a dose reduction following recovery to Grade 1 (or baseline) and optimal medical care |

AE, adverse event.

^a Study treatment dose adjustment is only needed if the toxicity was deemed related to study treatment or had an unclear relationship to study treatment.

^b For dose reduction levels, see Table 1.

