6.1.5 CRITERIA TO RESUME CABOZANTINIB TREATMENT

Subjects may resume treatment with cabozantinib when the drug-related AE(s) resolve to Grade \leq 1 or baseline value, with the following exceptions:

- Subjects may resume dosing in the presence of Grade 2 fatigue
- Subjects who delayed dosing due to UPCR \geq 2.0 or urine dipstick protein \geq 3+ may resume dosing at one dose level reduction when 24 hours urine protein $<$ 2.0 g or repeat UPCR $<$ 2.0
- Subjects who delayed dosing due to Grade 3 hypertension may resume dosing at the same dose or at one dose level reduction, at the discretion of the investigator, when hypertension has improved to Grade \leq 2.
- Subjects who delayed dosing due to Grade 4 lipase abnormalities (either asymptomatic or in the absence of radiographic findings) may resume dosing upon resolution to Grade \leq 2.
- Subjects who delayed dosing due to major surgery should not resume cabozantinib until complete wound healing has taken place. Following cabozantinib resumption, subjects should be monitored for wound dehiscence, wound infections, and other signs of impaired wound healing.

If treatment is delayed 8 weeks for any reason, the participant must be permanently discontinued from study therapy, except in cases where permission to resume treatment is granted by the Medical Monitor or designee.

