6.1.6 PERMANENT DISCONTINUATION OF CABOZANTINIB DUE TO ADVERSE EVENTS

Cabozantinib administration should be discontinued if at least one of the following drug-related adverse event(s) occurs:

- Subject no longer experiences clinical benefit as determined by the investigator. If study treatment is withdrawn for this reason, the date of this decision is to be recorded and every effort should be made to continue safety evaluations and collection of subsequent treatment information and follow-up information for survival.
- Unacceptable side effects the investigator feels may be due to study treatment, including any subject with a GI or non-GI perforation/fistula
- Any adverse event, laboratory abnormality or intercurrent illness, which, in the judgment of the Investigator, presents a substantial clinical risk to the subject with continuing study medication.
- Any Grade 3 non-skin, drug-related adverse event lasting $>$ 21 days
Exception of grade 3 drug-related AE:
 - Grade 3 drug-related laboratory abnormalities do not require treatment discontinuation except:
- Any drug-related Grade 4 drug-related adverse event or laboratory abnormality, except for the following events which do not require discontinuation:
 - Grade 4 neutropenia $<$ 7 days;

- Grade 4 lymphopenia or leukopenia;
- Grade 4 amylase or lipase abnormalities that are not associated with symptoms or clinical manifestations of pancreatitis;
- Isolated Grade 4 electrolyte imbalances/abnormalities that are not associated with clinical sequelae and are corrected with supplementation/appropriate management within 72 hours of their onset;
- The investigator feels it is not in the best interest of the subject to continue on study
- Participation in another clinical study using an investigational agent or investigational medical device
- Necessity for treatment with non-protocol systemic anticancer therapy
- Receipt of liver-directed local anti-cancer therapy (eg, transarterial tumor embolization or chemoembolization, radiofrequency or microwave ablation, percutaneous ethanol or acetic acid ablation, injection or infusion of drug eluting or radiation-emitting beads, cryoablation, radiation therapy, including stereotactic radiotherapy, or surgery)
- Necessity for withholding study drug for greater than 8 weeks for AEs, unless continuation of treatment is approved by the Principal Investigator

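### Table 4's first-row blood pressure test says *or* where *and* is needed: read literally, it asks for no cabozantinib reduction when only one component stays raised on optimal therapy

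*Protocol*

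**What the plan says.** Table 4 in Protocol section 6.1.4.8 has two rows defined by blood pressure.

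- **First row.** A patient enters when either component is raised: systolic above 150 but below 160, or diastolic above 100 but below 110 mm Hg. Antihypertensives are to be optimised. Cabozantinib goes down one level on this condition: "optimal antihypertensive therapy (usually to include 3 agents) does not result in BP < 150 mm Hg systolic or < 100 mm Hg diastolic". A further line reads "If subject is symptomatic interrupt study treatment".
- **Severe row.** Entry is at 160 systolic or 110 diastolic and above, again on either component. The first action has no condition: "Reduce study treatment by 1 dose level". The 150/100 test is then repeated with the same *or*, and if it is failed, "study treatment should be dose reduced further or interrupted". The next bullet interrupts dosing for sustained readings in the severe range that cannot be adequately managed, for readings above 180 or 120, and for symptoms. The restart line permits re-escalation only when systolic is below 140 *and* diastolic is below 90.

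Footnote a to the table lets the investigator start or adjust antihypertensives below 150 or 100, again naming each component separately. Among the exclusion criteria, section 5.2.1 lists "Uncontrolled hypertension defined as sustained BP > 150 mm Hg systolic, or 100 mm Hg diastolic despite optimal antihypertensive treatment".

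**The concern.** A patient enters the first row on one raised component, but by the literal wording is reduced only when both components have failed. Someone on about three antihypertensives with a systolic of 155 and a diastolic of 85 is in the row and passes the test. The same sustained state would have kept that patient out of the trial under section 5.2.1.

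Sites have some reason to take the word as written. The same table uses *and* in the restart line, where both components are wanted, and section 3.1 asks for strict adherence to the protocol's specifications. At stake is a dosing-safety step for a known class effect of the drug. From the starting dose, one level is 60 to 40 mg, or 1 − 40/60 = 33% of the daily dose.

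**Working it through.** The plan gives no figure to reproduce here. The check is one of logic, followed by a rough scale.

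**1. The test.** Let S be systolic and D diastolic on optimal therapy.

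- As written: reduce if NOT(S < 150 or D < 100). This equals S ≥ 150 and D ≥ 100, so both must fail.
- With *and*: reduce if NOT(S < 150 and D < 100). This equals S ≥ 150 or D ≥ 100, so either failure is enough.
- Section 5.2.1 counts as uncontrolled: S > 150 or D > 100.

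| Reading on optimal therapy | In first row | Reduce, as written | Reduce, with *and* | Uncontrolled by 5.2.1 |
|---|---|---|---|---|
| 155/85 | yes | no | yes | yes |
| 145/105 | yes | no | yes | yes |
| 155/105 | yes | yes | yes | yes |
| 145/85 | no | no | no | no |

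**2. All first-row readings.** Take whole-number readings with S from 120 to 159 and D from 60 to 109.

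- In the row: 9 × 50 + 9 × 40 − 9 × 9 = 729.
- Test as written fires for 10 × 10 − 1 = 99 of them. With *and* it fires for all 729.
- Readings with only one component above its entry limit: 729 − 81 = 648. The test as written fires for 18 of these. In all 18 the other component is exactly 150 or 100, so it too is not below target.

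The literal test therefore never fires when one component is below its target. These are counts of possible readings, not patient proportions.

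**3. Severe row.** The first reduction is unconditional, so the repeated *or* affects only the further reduction or interruption. Sustained, unmanageable readings at or above 160 or 110 are caught by the next bullet. What remains is a patient already reduced once and brought down to, say, 155/85.

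**4. Scale.** Section 1.2.2 gives phase 3 rates of 29% for hypertension of any grade and 16% for Grade 3. The planned sample is 40.

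- Any grade: 0.29 × 40 = 11.6 expected (binomial 95% range 6 to 17).
- Grade 3: 0.16 × 40 = 6.4 expected (range 2 to 11).
- If Grade 3 corresponds to the severe row, where one reduction is automatic, the first-row base is 11.6 − 6.4 = 5.2.
- The share of these left with one raised component on optimal therapy is not known. At an assumed 10%, 25% or 50%: 5.2 × 0.10 = 0.5; 5.2 × 0.25 = 1.3; 5.2 × 0.50 = 2.6 patients.

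**The case against.** The strongest reply is that the intent is plain. Row entry, footnote a and the exclusion criterion all treat either raised component as a problem, so most clinicians would read the line as requiring both to be controlled. That is right about intent, and it makes this a drafting slip rather than a chosen policy. It does not make the wording correct.

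A reader might infer that such a patient gets no required action, or that a reduction is barred. The documents do not support either. Antihypertensives must still be optimised, symptomatic patients are interrupted, and pressure is checked at each visit and daily at home. Table 2 in section 6.1.4.1 gives the investigator discretion to reduce or interrupt for "Grade 2 AEs which are intolerable and cannot be adequately managed". For Grade 3 events it calls for interruption unless a dose reduction and medical care can easily manage the toxicity. Section 6.1.6 provides for stopping when an event "presents a substantial clinical risk to the subject with continuing study medication". These limits stand. What they leave open is an asymptomatic patient whose event is not Grade 3: there, a reduction depends on discretion. Whether 155/85 on three agents would be Grade 3 cannot be settled here, because the protocol refers out for its grading criteria and gives no mm Hg cut-offs.

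It is also tempting to use all 11.6 expected hypertensive patients as the base. Under the mapping above, that would include the 6.4 who already receive an unconditional reduction. Even 5.2 may be too high, since some of those patients may never exceed 150/100.

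**Conclusion.** The point holds as a wording error in a dosing-safety rule. Read literally, Table 4 omits a required one-level reduction for an asymptomatic patient with one component still above the protocol's own limit on optimal therapy. The logic needs no assumption. The scale of 0.5 to 2.6 patients rests on three: that the phase 3 rates carry over, that Grade 3 corresponds to the severe row, and that 10% to 50% of the remainder keep one raised component.

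The rule governs dose. It does not change how events are graded or counted, so the error rates, the power and the critical adverse event count are unaffected. A reader might infer an effect on discontinuations due to adverse events, which are among the primary outcomes. The documents give neither a direction nor a size for one.

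A reader might also see a breach in section 6.1.5, under which patients held for Grade 3 hypertension "may resume dosing at the same dose or at one dose level reduction, at the discretion of the investigator". After an immediate hold, the last dose taken is the dose before the event. The re-escalation conditions in section 6.1.4.1 and Table 4 presuppose an earlier reduction, so restarting at that dose does not breach them. The only real tension is with the severe row's unconditional reduction. The two texts can be read together: reduce under Table 4, then resume at that dose or one level lower. The manufacturer's recommendations, to which the protocol defers, may settle it but are not reproduced. This merits a clarification at most.

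**What to change.** In both Table 4 tests, state the target as systolic below 150 mm Hg *and* diastolic below 100 mm Hg. Check the result against the manufacturer's recommendations.

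This is a one-word amendment in two places, with no new assessments. A few patients with one raised component would be reduced who would not be under the literal text, and investigators lose a little discretion for them.

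Optionally, add a sentence to section 6.1.5 saying that, after an immediate hold under the severe row, the same dose means the dose after that row's one-level reduction.

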6.1.4.9 THROMBOEMBOLIC EVENTS

Thromboembolic complications are frequent in cancer patients due to procoagulant changes induced by the malignancy or anticancer therapy including inhibitors of VEGF pathways. DVT and PE have been observed in clinical studies with cabozantinib; including fatal events (please refer to the Investigator's Brochure). Subjects who develop a PE or DVT should have study treatment held until therapeutic anticoagulation with heparins (LMWH) is established. (Note: therapeutic anticoagulation with oral anticoagulants is prohibited.) Study treatment may be resumed in subjects with PE or DVT if it is determined that the event is uncomplicated, they are deriving benefit from study treatment, and that anticoagulation does not place them at a significant risk that outweighs the benefit of resuming treatment. During treatment with anticoagulants, subjects need to be monitored on an ongoing basis for bleeding risk and signs of bleeding. Subjects with life-threatening PE or DVT should have study treatment discontinued unless toxicity can be managed and subject is deriving clear clinical benefit as

determined by the investigator. Subjects who develop portal/hepatic vessel thrombosis may not require anticoagulation. The decision regarding anti-coagulation in such cases is at the discretion of the investigator and within the context of standard of care. Arterial thrombotic events (eg, transient ischemic attack, myocardial infarction) have been observed rarely in studies with cabozantinib. Subjects should be evaluated for preexisting risk factors for arterial thrombotic events such as diabetes mellitus, hyperlipidemia, hypertension, coronary artery disease, history of tobacco use, and cardiac or thromboembolic events that occurred prior to initiation of study treatment. Study treatment should be discontinued in subjects who develop an acute myocardial infarction or any other clinically significant arterial thromboembolic complication.

6.1.4.10 PROTEINURIA

Proteinuria is an anticipated AE with the inhibition of VEGF pathways and has been observed in cabozantinib clinical studies, and nephrotic syndrome has been reported with cabozantinib and other inhibitors of VEGF pathways. During each safety assessment visit, proteinuria will be quantified by measuring the urine protein-to-creatinine (UPCR) ratio performed by the central lab. In addition, urine dipstick analysis performed by the local lab will be done at least every 8 weeks and more as clinically indicated. Management of proteinuria will be based on UPCR results provided by the central lab. As dipstick results from the local labs may be available prior to the UPCR results from the central lab, they can be used by the investigator for interim management. In the case of proteinuria, if the dipstick analysis shows proteinuria $\geq 3+$, study treatment should be interrupted until the UPCR results are available and more definitive management can be applied.

6.1.4.11 CORRECTED QTc PROLONGATION

The effect of orally administered cabozantinib at 140 mg/day (FBE) on QTc interval was evaluated in a randomized, double-blinded, placebo-controlled Phase 3 study in patients with MTC (Study XL184-301). A mean increase in QT interval corrected by Fridericia (QTcF) of 10-15 ms was observed at 4 weeks after initiating cabozantinib. A concentration-QTc relationship could not be definitively established. Changes in cardiac wave form morphology or new rhythms were not observed. No cabozantinib treated patients on this study had a QTcF > 500 ms during the QT evaluation period.

Only subjects with a baseline QTcF ≤ 500 ms are eligible for this study. Subjects will have ECGs performed at times designated by the protocol. If at any time on study there is an increase in QTcF interval to an absolute value > 500 ms, within 30 minutes after the initial ECG, 2 additional ECGs must be performed each with intervals approximately 3 minutes apart. If the average QTcF from the 3 ECGs is > 500 ms, the following actions must be taken:

- Withhold study treatment
- Immediately notify the Principal Investigator
- Hospitalize symptomatic subjects (eg, with palpitations, dizziness, syncope, orthostatic hypotension, a significant ventricular arrhythmia on ECG) for a thorough cardiology evaluation and management

- Consider cardiology consultation for asymptomatic subjects for evaluation and management
- Check electrolytes, especially magnesium and potassium; correct abnormalities as clinically indicated
- Check concomitant medications for any medication that may have contributed to QT prolongation, and if possible, discontinue these medications (see <http://www.qtdrugs.org>)
- Send ECGs to central ECG laboratory (see ECG study manual)
- Repeat ECG triplicates hourly until the average QTcF is \leq 500 ms. Study treatment may be restarted at a reduced dose level if all of the following conditions are met:
 - Symptoms are determined to be unrelated to the QT interval prolongation
 - The QTcF value $>$ 500 ms is not confirmed by the central ECG laboratory or a QTcF $>$ 500 ms confirmed by the central laboratory returns to \leq 500 ms
- Study treatment has been interrupted through a minimum of 1 week following the return of the QTcF to \leq 500 ms

Study treatment must be permanently discontinued if either of the following applies:

- Cardiac evaluation confirms that symptoms are the consequence of QT interval prolongation
- Recurrence of QTcF prolongation (confirmed by central ECG lab) after reinitiation of study treatment at a reduced dose

